## **1.2 Rationale for study design, doses and control groups**

This is a regional study designed to investigate the safety and efficacy of the fixed dose benralizumab (30 mg) administered subcutaneously (SC) every 4 weeks for the first 3 doses and then every 8 weeks thereafter in exacerbation-prone asthma patients who remain uncontrolled on medium to high-doses ICS-LABA with or without oral corticosteroids and other asthma controller(s).

Primary efficacy will be determined based on reduction in the rate of asthma exacerbations over 48 weeks for benralizumab versus placebo. In order to avoid biasing the results, the study will be randomised and double-blinded with stratification by age group (adult or adolescent), country/region and eosinophil category ( $\geq 300/\mu\text{L}/< 300/\mu\text{L}$ ).

The study will randomise patients with screening blood eosinophils  $\geq 300/\mu\text{L}$  and  $< 300/\mu\text{L}$  at a ratio of about 2:1. The 2:1 stratification of patients with eosinophil counts  $\geq 300/\mu\text{L}$  and  $< 300/\mu\text{L}$  is intended as a means of enriching the population for patients most likely to respond to benralizumab (ie,  $\geq 300/\mu\text{L}$ ), while still accommodating patients below this threshold in order to help understand where additional benefit drops off.

The benralizumab dose (30 mg SC, fixed) and the maintenance regimens are based on all available safety, efficacy and immunogenicity data, as well as population exposure-response modeling, and stochastic trial simulations from earlier phase benralizumab trials. In particular, Phase 2b MI-CP220 study (Castro et al 2014) showed that fixed doses of

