#### **3.1 Inclusion criteria\***

For inclusion in the study patients should fulfil all of the following criteria:

- 1 Written informed consent, and assent when applicable for study participation must be obtained prior to any study related procedures being performed (local regulations are to be followed in determining the assent/consent requirements for children and parent[s]/guardian[s]) and according to international guidelines and/or applicable local guidelines.
- 2 Female and male aged 12 to 75 years, inclusively, at the time of Visit 1
  - For those patients, who are 17 on the day of Visit 1 but will turn 18 after this day, will be considered an adolescent for the purposes of this trial
- 3 Women of childbearing potential (WOCBP) must agree to use a highly effective method of birth control (confirmed by the Investigator) from enrolment, throughout the study duration and within 12 weeks after last dose of IP and have negative serum pregnancy test result on Visit 1. Highly effective methods (those that can achieve a failure rate of less than 1% per year when used consistently and correctly) include: combined (estrogen and progestogen containing) hormonal contraception associated with inhibition of ovulation- oral, intravaginal, or transdermal; progestogen-only hormonal contraception associated with inhibition of ovulation- oral, injectable, or implantable; intrauterine device (IUD); intrauterine hormone-releasing system (IUS); bilateral tubal occlusion; sexual abstinence, i.e. refraining from heterosexual intercourse (The reliability of sexual abstinence needs to be evaluated in relation to the duration of the clinical study and the preferred and usual lifestyle of the patient); vasectomized sexual partner provided that partner is the sole sexual partner of the WOCBP study patient and that the vasectomized partner has received medical assessment of the surgical success.

Women not of childbearing potential are defined as women who are either permanently sterilized (hysterectomy, bilateral oophorectomy, or bilateral salpingectomy), or who are postmenopausal. Women will be considered postmenopausal if they have been amenorrhic for 12 months prior to the planned date of randomisation without an alternative medical cause. The following age-specific requirements apply:

- Women <50 years old will be considered postmenopausal if they have been amenorrhic for 12 months or more following cessation of exogenous hormonal

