### **3.3 Patient enrolment and randomisation**

Investigator(s) should keep a record of patients considered for and included in the study. This pre-screening/screening log will be evaluated periodically by AstraZeneca or its delegates during routine monitoring visits.

Each patient should meet all of the inclusion criteria and none of the exclusion criteria for this study. Under no circumstances can there be exceptions to this rule.

The Investigator or designee will:

- 1 Obtain signed informed consent, and assent when applicable, from the potential patient before any study specific procedures are performed.
- 2 Assign each potential patient a unique enrolment number, beginning with 'E#' via interactive web/voice response system (IWRS/IVRS).
- 3 Determine patient's eligibility.
- 4 Assign eligible patient unique randomisation code via IWRS/IVRS.

Patients will be allocated to receive benralizumab or placebo in a 1:1 ratio. The randomisation will be stratified by country/region, age group (adult or adolescent), and blood eosinophil count at Visit 1 ( $\geq 300/\mu\text{L}$  or  $< 300/\mu\text{L}$ ) and the randomisation numbers will be grouped in blocks. The  $< 300/\mu\text{L}$  stratum will be closed when the total number of patients in the stratum hits approximately 222. When a stratum is full, patients who fall within that stratum will not be randomised and will be withdrawn from the study (see Section 3.10.2).

Randomised patients, who discontinue from IP or withdraw from study, will not be replaced. If a patient withdraws from the study, then his/her enrolment number/randomisation code cannot be reused.

Specific information concerning the use of the IWRS/IVRS will be provided in the separate manual.

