### 8.2 Sample size estimate

The study will randomise patients with baseline blood eosinophil counts  $\geq 300/\mu\text{L}$  and  $< 300/\mu\text{L}$  at a ratio of about 2:1. The 2:1 stratification ratio is intended as a means of enriching the population for patients most likely to respond to benralizumab (i.e.,  $\geq 300/\mu\text{L}$ ), while still including patients below this threshold in order to help understand efficacy and safety in this group. The study is powered for the primary efficacy analysis of the patients with baseline blood eosinophils  $\geq 300/\mu\text{L}$ .

The efficacy analyses will comprise both adults and adolescent patients.

For the primary endpoint annual asthma exacerbation rate, approximately 222 adults and adolescent patients with baseline blood eosinophil counts  $\geq 300/\mu\text{L}$  per treatment arm (approximately 444 in total) will need to be randomised to achieve approximately 90% power

CCI

As stated

previously an about 2:1 ratio will be used for patients with baseline blood eosinophil counts  $\geq 300/\mu\text{L}$  and  $< 300/\mu\text{L}$ . Therefore the study will also randomise approximately 111 patients/arm (approximately 222 in total) with baseline blood eosinophil counts  $< 300/\mu\text{L}$ . The  $< 300/\mu\text{L}$  stratum will be closed for all patients, when a total of 222 adults and adolescent patients have been randomised in the stratum. So a total of approximately 666 adult and adolescent patients are expected to be randomised in the study. Among these 666 patients, at least 70% patients will be randomised from China.

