### **8.5.1 Analysis of the primary variable (s)**

The primary efficacy variable is the annual asthma exacerbation rate and the primary analysis is to compare the annual asthma exacerbation rate of benralizumab group with placebo group in patients with baseline blood eosinophil counts  $\geq 300/\mu\text{L}$ .

The null hypothesis is that the exacerbation rate on benralizumab is equal to the exacerbation rate on placebo. The alternative hypothesis is that the exacerbation rate on benralizumab is not equal to the exacerbation rate on placebo, ie,

*H0: Rate ratio (benralizumab vs. Placebo) = 1*

*Ha: Rate ratio (benralizumab vs. Placebo)  $\neq 1$*

Exacerbation rate in the benralizumab group will be compared to exacerbation rate in the placebo group using a negative binomial model. The response variable in the model will be the number of asthma exacerbations over the 48-week treatment period. The model will include covariates of treatment group, region (China/non-China), number of exacerbations in the year before the study, and the use of maintenance oral corticosteroids (yes/no). The logarithm of the follow-up time will be used as an offset variable in the model.

The estimated treatment effect (i.e., the rate ratio of benralizumab versus placebo), corresponding 95% confidence interval (CI), and two-sided p-value for the rate ratio will be presented. In addition, the exacerbation rate and the corresponding 95% CI within each treatment group will be presented.

In addition, the exacerbation rate will also be summarized in patients with baseline blood eosinophil counts  $< 300/\mu\text{L}$ ,  $< 150/\mu\text{L}$ ,  $150\text{-}299/\mu\text{L}$ ,  $300\text{-}449/\mu\text{L}$  and  $\geq 450/\mu\text{L}$  separately.

The individual exacerbation criteria (ER visit due to asthma that required systemic corticosteroids, hospitalization due to asthma, or use of systemic corticosteroids) will also be summarized.

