### **8.5.2 Analysis of the secondary variable(s)**

#### **8.5.2.1 Analysis methods for secondary efficacy variables**

Key secondary efficacy endpoints in this study are:

- Change from baseline in pre-bronchodilator FEV1 at Week 48
- Change from baseline in asthma symptom total score at Week 48

Other secondary efficacy endpoints include

- Proportion of patients with  $\geq 1$  asthma exacerbation
- Time to the first asthma exacerbation

- Annual rate of asthma exacerbations that are associated with an emergency room/urgent care visit or a hospitalization
- Change from baseline in total rescue medication use (average puffs/day)
- Change from baseline in morning and evening PEF at Week 48
- Change from baseline in asthma symptom day time/night time scores at Week 48
- Change from baseline in number of nights with awakening due to asthma and requiring rescue medication
- ACQ-6
- SGRQ

All the secondary efficacy endpoints will be analysed in patients with baseline blood eosinophil counts  $\geq 300/\mu\text{L}$ . In addition, the 2 key secondary efficacy endpoints will be analysed in patients with baseline blood eosinophil counts  $< 150/\mu\text{L}$ ,  $< 300/\mu\text{L}$ ,  $150\text{-}299/\mu\text{L}$ ,  $300\text{-}449/\mu\text{L}$  and  $\geq 450/\mu\text{L}$  separately.

Change from baseline in pre-bronchodilator FEV1 at Week 48 will be compared between the benralizumab group and placebo using a repeated measures analysis on patients with a baseline pre-bronchodilator FEV1 and at least 1 post-randomisation pre-bronchodilator FEV1 in the full analysis set. The dependent variable will be the change from baseline in pre-bronchodilator FEV1 at post-baseline protocol-specified visits (up to the EOT Visit). Treatment group will be fitted as the explanatory variable, and region (China/non-China), baseline pre-bronchodilator FEV1, visit, the interaction term of visit and treatment, and the use of maintenance oral corticosteroids (yes/no) will be fitted as covariates. Visit will be fitted as a categorical variable, and the variance-covariance matrix will be assumed to be unstructured. If the procedure does not converge then a compound symmetric variance-covariance matrix will be used instead. The model is:

*Change in FEV1 = Treatment group + baseline FEV1 + region + maintenance oral corticosteroids + visit + treatment \* visit*

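### Randomisation is stratified by age group, but the primary and key secondary models leave age group out without giving a reason (minor)

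*Supplement*

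**What the plan says.** Stratification is stated in the protocol's Section 3.3, "The randomisation will be stratified by country/region, age group (adult or adolescent), and blood eosinophil count at Visit 1", and again in the design rationale of Section 1.2, "the study will be randomised and double-blinded with stratification by age group (adult or adolescent), country/region and eosinophil category". Both age strata are open, since Section 3.1 admits "Female and male aged 12 to 75 years, inclusively, at the time of Visit 1". They are pooled for efficacy under Section 8.2: "The efficacy analyses will comprise both adults and adolescent patients".

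The models are specified as follows.

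- **Primary, negative binomial (Section 8.5.1).** "The model will include covariates of treatment group, region (China/non-China), number of exacerbations in the year before the study" The same sentence continues "and the use of maintenance oral corticosteroids (yes/no). The logarithm of the follow-up time will be used as an offset variable in the model".
- **Key secondary, FEV1 repeated measures (Section 8.5.2.1).** "Treatment group will be fitted as the explanatory variable, and region (China/non-China), baseline pre-bronchodilator" FEV1, then "visit, the interaction term of visit and treatment, and the use of maintenance oral corticosteroids (yes/no) will be fitted as covariates". The model equation is also written out, without age.
- **Key secondary, asthma symptom total score (Section 8.5.2.1).** A model similar to the one for FEV1.
- **Other secondary analyses (Section 8.5.2.1).** The Cochran–Mantel–Haenszel test, the Cox model and the logistic responder models each have their own list. None contains age group.

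Age appears in Section 8.5.3, in three bands, among the subgroup factors for the primary variable. That analysis is labelled exploratory.

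**The concern.** Of the three stratification factors, two reach the analysis. Eosinophil category is dealt with by restricting the primary analysis to patients at or above 300/µL, and country/region is carried as China/non-China. Age group is carried in no form.

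Stratified allocation balances age group between the arms. If age group predicts outcome, a model that ignores it takes no credit for that balance: the between-age-group variation stays in the residual or dispersion term, and the standard error of the treatment effect is somewhat larger than it need be. At stake is a little precision in the three tests that make up the alpha-controlled family of Section 8.5.

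The amendment history explains why country was collapsed (few patients outside China). Neither it nor the current text explains why age group is absent.

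**Working it through.** **1. The plan's own figure.** Section 8.2 gives about 222 patients per arm (444 in total) for about 90% power. The effect size and dispersion are blacked out, so this cannot be reproduced as such. The placebo rate of 0.88 per year stands only in the amendment history. For a negative binomial comparison,

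var(log RR) = [1/(t·r0) + k + 1/(t·r1) + k] / n,

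with n = 222, t = 48×7/365.25 = 0.92 years, r0 = 0.88, r1 = RR·r0 and two-sided alpha 0.05. Under this formula 90% power corresponds to a rate ratio of 0.66 (k = 0.3), 0.62 (k = 0.8), 0.61 (k = 1.0) or 0.55 (k = 2.0). All these k are assumed.

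**2. Variance lost by omitting age group.** Assume RR = 0.60, so r1 = 0.528. The dispersion that then gives 90% power is k = 1.11; it is back-solved and is not a design input. The bracket is

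1/(0.88×0.92) + 1/(0.528×0.92) + 2×1.11 = 1.235 + 2.059 + 2.220 = 5.51.

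If a share p of patients are adolescents with rate ratio g to adults, age adds about p(1−p)(ln g)² to the dispersion in each arm. Adjusting removes 2·p(1−p)(ln g)² from the bracket.

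| p | g | p(1−p)(ln g)² | Reduction in variance |
|---|---|---|---|
| 5% | 0.6 | 0.0475×0.261 = 0.012 | 0.025/5.51 = 0.45% |
| 10% | 0.6 | 0.09×0.261 = 0.023 | 0.047/5.51 = 0.85% |
| 10% | 0.4 | 0.09×0.840 = 0.076 | 0.151/5.51 = 2.7% |

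As required sample size is proportional to variance, this is worth about 2 to 12 of the 444 patients (0.0045×444 = 2.0; 0.027×444 = 12.0). The share p and ratio g are assumptions; the documents give neither.

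**3. Simulation.** Negative binomial counts were generated for N = 444 with 1:1 allocation balanced within age group, k = 0.8, complete 48-week follow-up and an overall placebo rate of 0.88. Models with and without age group were fitted to the same data sets. Power at RR = 0.60, 2000 runs each:

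| p | g | Without age | With age | Gain (points) |
|---|---|---|---|---|
| 5% | 0.5 | 93.60% | 93.90% | 0.30 |
| 5% | 2.0 | 93.20% | 93.35% | 0.15 |
| 10% | 0.5 | 94.30% | 94.65% | 0.35 |
| 10% | 2.0 | 92.80% | 93.20% | 0.40 |

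Type I error with 6000 runs, without versus with age group:

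- p = 5%, g = 2.0: 0.052 versus 0.053
- p = 10%, g = 0.5: 0.056 versus 0.056
- p = 10%, g = 2.0: 0.049 versus 0.051

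The average estimated rate ratio agreed to about 0.001 between the two models.

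**4. FEV1 and symptom score.** The documents give neither a standard deviation of change nor an adult–adolescent difference in change, so no comparable figure can be derived for these endpoints.

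**The case against.** The strongest reply is that the effect is negligible, and on size that is nearly right. Both calculations credit age with its full marginal prognostic value, whereas the primary model already contains prior-year exacerbations and maintenance oral corticosteroid use. If age is correlated with either, the real gain is smaller, so the figures above are closer to a ceiling. A sparse adolescent stratum would also be a fair reason to leave the factor out, as sparsity was for country. What remains is that the plan gives no such reason. Nor is the matter left open for the SAP, because the protocol itself fixes the covariate lists.

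Section 1.2 of the protocol describes asthma manifestations and treatment responses in adolescents and adults as similar. It does so to support giving adolescents the adult dose, and it stands beside a decision to stratify by age.

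A reader might infer more than the documents support:

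- **That age is in no efficacy model.** Section 8.5.3 does model it for the primary variable, though only as an exploratory analysis that adjusts neither the primary nor the key secondary estimates.
- **That the omission biases the estimate or inflates type I error.** It does not. Randomisation balances the factor, and any effect is mildly conservative.
- **That FEV1 is specially at risk because adolescents enter on a different limit (below 90% rather than 80% predicted) or are still growing.** The entry limit concerns baseline level, and baseline FEV1 is already a covariate. The documents give no growth figure, and the stratification balances growth between arms.
- **That the same precision argument covers the Cox and logistic models.** It does not. There, adding a prognostic covariate changes the conditional estimand, because hazard and odds ratios are non-collapsible, and it does not reduce the standard error of the treatment coefficient.

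**Conclusion.** The omission is plain from the text: age group is a stratification factor, and it is absent from the primary negative binomial model and from both key secondary repeated-measures models, with no reason given. The consequence is minor. It is a small loss of precision, not a threat to validity: about 0.5–2.7% of the variance of the log rate ratio at most, or about 0.2–0.4 points of power. No change in sample size follows.

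The covariate lists can be checked directly, so confidence in the omission is high. The size rests on an assumed adolescent share, age effect, rate ratio and dispersion, and on a placebo rate found only in the amendment history.

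**What to change.** Add age group (adult/adolescent, as randomised) as a covariate to the primary negative binomial model and to the repeated-measures models for FEV1 and asthma symptom total score. Pre-specify a rule for dropping it where the adolescent stratum is too sparse for the model to be fitted, which matters most in the narrow eosinophil bands. The threshold should be set and justified before unblinding. If the sponsor prefers to keep age group out, state the reason and pre-specify an age-adjusted sensitivity analysis for these three endpoints.

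For the Cox and logistic models, adding it for consistency is optional. If it is added, note that the hazard and odds ratios are then conditional on age group.

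The cost is one degree of freedom per model and a small edit to the covariate lists and programs. Section 8.1 allows final SAP amendments up to unblinding. Sample size, randomisation and conduct are unaffected.

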### **8.5.2 Analysis of the secondary variable(s)**

#### **8.5.2.1 Analysis methods for secondary efficacy variables**

Key secondary efficacy endpoints in this study are:

- Change from baseline in pre-bronchodilator FEV1 at Week 48
- Change from baseline in asthma symptom total score at Week 48

Other secondary efficacy endpoints include

- Proportion of patients with  $\geq 1$  asthma exacerbation
- Time to the first asthma exacerbation

- Annual rate of asthma exacerbations that are associated with an emergency room/urgent care visit or a hospitalization
- Change from baseline in total rescue medication use (average puffs/day)
- Change from baseline in morning and evening PEF at Week 48
- Change from baseline in asthma symptom day time/night time scores at Week 48
- Change from baseline in number of nights with awakening due to asthma and requiring rescue medication
- ACQ-6
- SGRQ

All the secondary efficacy endpoints will be analysed in patients with baseline blood eosinophil counts  $\geq 300/\mu\text{L}$ . In addition, the 2 key secondary efficacy endpoints will be analysed in patients with baseline blood eosinophil counts  $< 150/\mu\text{L}$ ,  $< 300/\mu\text{L}$ ,  $150\text{-}299/\mu\text{L}$ ,  $300\text{-}449/\mu\text{L}$  and  $\geq 450/\mu\text{L}$  separately.

Change from baseline in pre-bronchodilator FEV1 at Week 48 will be compared between the benralizumab group and placebo using a repeated measures analysis on patients with a baseline pre-bronchodilator FEV1 and at least 1 post-randomisation pre-bronchodilator FEV1 in the full analysis set. The dependent variable will be the change from baseline in pre-bronchodilator FEV1 at post-baseline protocol-specified visits (up to the EOT Visit). Treatment group will be fitted as the explanatory variable, and region (China/non-China), baseline pre-bronchodilator FEV1, visit, the interaction term of visit and treatment, and the use of maintenance oral corticosteroids (yes/no) will be fitted as covariates. Visit will be fitted as a categorical variable, and the variance-covariance matrix will be assumed to be unstructured. If the procedure does not converge then a compound symmetric variance-covariance matrix will be used instead. The model is:

*Change in FEV1 = Treatment group + baseline FEV1 + region + maintenance oral corticosteroids + visit + treatment \* visit*

Change from baseline in asthma symptom total score; day time score, and night time score at Week 48 will be analysed separately using a similar model as the above model for change from baseline in pre-bronchodilator FEV1.

The proportion of patients with  $\geq 1$  asthma exacerbation during the 48 weeks of treatment will be addressed as a supportive variable to the primary objective. The proportion in the benralizumab group will be compared with the proportion in the placebo group using a Cochran–Mantel–Haenszel test controlling for region (China/non-China), number of exacerbations in the year before the study, and the use of maintenance oral corticosteroids (yes/no).

Time to first asthma exacerbation will be analysed as another supportive efficacy variable to the primary objective to explore the extent to which treatment with benralizumab delays the time to first exacerbation compared with placebo. A Cox proportional hazard model will be fitted to data with the covariates of treatment, region (China/non-China), number of exacerbations in the year before the study, and the use of maintenance oral corticosteroids (yes/no).

Annual rate of asthma exacerbations that are associated with an emergency room/urgent care visit or a hospitalization will be analysed using a similar negative binomial model as outlined for the primary efficacy variable in Section 8.5.1.

Change from baseline in total rescue medication use (average puffs/days) and number of nights with awakening due to asthma and requiring rescue medication will be analysed using a similar model as for change from baseline in pre-BD FEV1.

Change from baseline in morning and evening PEF at Week 48 will be analysed separately using similar models as the model for change from baseline in pre-BD FEV1.

The ACQ-6 will be analysed in terms of change from baseline to end of treatment, change from baseline to each of post-randomisation periods, responder status at EOT (i.e. change from baseline to EOT  $\leq -0.5$ ), and asthma symptom control status at EOT (see Section 8.4.3.2 for categorization).

The SGRQ will be analysed in terms of change from baseline to end of treatment, change from baseline to each of post-randomisation periods in total score and three domain scores, and responders as defined by those with a SGRQ total score  $\geq 4$  unit decrease from baseline at EOT.

Change in mean score from baseline for ACQ-6 and change in total score from baseline for SGRQ (including the domain scores) will be analysed using a similar model as for change from baseline in pre-BD FEV1.

Responder variables for ACQ-6 (yes/no) and SGRQ (yes/no) will be analysed using a logistic regression model with covariates of treatment, region (China/non-China), baseline value, and the use of maintenance oral corticosteroids (yes/no).

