#### 8.4.3.4 Electronic diary variables

Asthma PROs (ACQ-6, SGRQ), and daily metrics (rescue medication, awakenings and peak flow and asthma symptom scores) derived from the Asthma Daily Diary will be summarized as the mean for baseline and each of the post-randomisation periods.

Biweekly (14 days) means will be calculated for daily assessments of asthma symptoms, night time awakenings, rescue medication usage and peak flow. Baseline will be the 14 days prior to randomisation and will be summarized as a mean. Post-randomisation biweekly (14 day) means will be calculated for each daily assessment and then summarized as group means for each 14-day period post-randomisation. ACQ-6 and SGRQ baseline will be the last observation prior to study drug administration and summarized as mean scores for each group. The change from baseline to each post-randomisation period will be used as secondary efficacy variable.

Rescue medication usage is captured in the daily diary as the number of inhaler puffs and the number of times a nebulizer is used. Rescue medication usage will be summarized as the number of puffs with 1 instance of nebulizer use converted to 2 puffs.

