### **8.5 Methods for statistical analyses**

The analysis of the primary and secondary endpoints will include all data captured during the 48-week treatment period regardless of whether study treatment was prematurely discontinued, or delayed, and/or irrespective of protocol adherence.

To control the type I error rate, a testing strategy will be applied to the primary (annual asthma exacerbation rate) and 2 key secondary endpoints (the change in FEV1 and asthma symptom score from baseline to Week 48, respectively) for patients with baseline blood eosinophil counts  $\geq 300/\mu\text{L}$  for benralizumab. The testing strategy will be according to the following gate keeping procedure:

*Step 1:* Perform the test of annual asthma exacerbation rate (benralizumab vs. placebo) at the family wise error rate (FWER) of 0.05. If the p-value is less than 0.05, then proceed to Step 2; otherwise no null hypothesis is rejected.

*Step 2:* Test the 2 key secondary endpoints at the FWER of 0.05 using a Holm Procedure (Holm 1979).

Demography and baseline characteristics will be summarized by treatment group for the full analysis set. In the event that there are major differences between the full analysis set and safety analysis set, these summaries will also be repeated for the safety analysis set.

Additional analyses assessing the impact of Cases of Civil Crisis, Natural Disaster, or Public Health Crisis (e.g. SARS-CoV-2) may be included in the SAP.

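### The key secondary model fits one baseline slope at all visits; adding baseline-by-visit is a cheap safeguard for the Week 48 tests

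*Supplement*

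**What the plan says.** Section 8.5.2.1 of the protocol sets out the FEV1 model in words and as an equation.

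- **Outcome:** "The dependent variable will be the change from baseline in pre-bronchodilator" FEV1 at each post-baseline visit up to end of treatment.
- **Fixed effects:** treatment, region, baseline FEV1, and then "visit, the interaction term of visit and treatment, and the use of maintenance oral corticosteroids (yes/no) will be fitted as covariates". In the equation, treatment and baseline FEV1 are followed by "region + maintenance oral corticosteroids + visit + treatment", the last of these crossed with visit. Treatment is the only term that interacts with visit.
- **Covariance:** "Visit will be fitted as a categorical variable, and the variance-covariance matrix will be assumed to be unstructured". The fallback is: "If the procedure does not converge then a compound symmetric variance-covariance matrix will be used instead".
- **Symptom scores:** total, daytime and night-time scores "will be analysed separately using a similar model as the above model for change from baseline in pre-bronchodilator" FEV1. Section 8.4.3.4 defines the repeated values: "Post-randomisation biweekly (14 day) means will be calculated for each daily assessment", which gives 48/2 = 24 periods.

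Rescue use, awakenings, PEF, ACQ-6 and SGRQ change scores are also referred to a similar model. Under Section 8.5, FEV1 and symptom total score at Week 48 are tested by the Holm procedure after the primary endpoint, in patients with eosinophils of at least 300/µL.

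**The concern.** The model lets the treatment effect differ by visit but holds the baseline adjustment constant. The alpha-controlled tests use one visit only, the last. The fitted slope is a weighted average over all visits, up to 24 of them for the symptom score. It is right at Week 48 only if the slope does not change over time.

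A changing slope is plausible from the design. The symptom baseline is the mean of the 14 days before randomisation, the first post-randomisation period follows directly, and Week 48 is about 11 months later. If the slope does change, two things follow. The Week 48 residual variance is larger than it need be. And if Week 48 data are missing in a way that depends on baseline and differs by arm, the misfit can leak into the treatment contrast.

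**Working it through.** **The plan's own figure.** There is none for these endpoints. The 222 per arm (444 in total) at about 90% power in Section 8.2 concerns the exacerbation rate. Its effect size is blacked out, so it cannot be re-derived, and nothing below depends on it.

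**Inputs.**
- From the protocol: the model terms, change as the outcome, 24 biweekly periods and about 444 patients.
- Assumed: the correlation r(t) between baseline and the value at visit t; equal SDs at all visits (set to 1); the within-patient residual covariance Σ; and spirometry at Weeks 4, 8, 16, 24, 32, 40 and 48 (the columns of Table 2 are broken in the extract).

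**Step 1: slope of change on baseline.** With equal SDs, b(t) = r(t) − 1. If r falls from 0.85 to 0.70, b moves from −0.15 to −0.30. So the link to the later *value* weakens, while the slope for *change* moves away from zero.

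**Step 2: cost at Week 48.** With a visit-specific slope the residual variance is 1 − r48². With a common slope it is (1 − r48²) + (b48 − bc)². Under unstructured covariance bc = 1'Σ⁻¹b / 1'Σ⁻¹1. The SE ratio is therefore √[1 + (b48 − bc)²/(1 − r48²)].

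| Endpoint | r: early → Week 48 | b48 | bc | Variance inflation | SE |
|---|---|---|---|---|---|
| FEV1 | 0.85 constant | −0.150 | −0.150 | 0 | 0 |
| FEV1 | 0.85 → 0.80 | −0.200 | −0.171 | 0.029²/0.36 = 0.2% | +0.1% |
| FEV1 | 0.85 → 0.75 | −0.250 | −0.184 | 0.066²/0.4375 = 1.0% | +0.5% |
| FEV1 | 0.85 → 0.70 | −0.300 | −0.190 | 0.110²/0.51 = 2.4% | +1.2% |
| FEV1 | 0.80 → 0.60 | −0.400 | −0.242 | 0.158²/0.64 = 3.9% | +1.9% |
| Symptoms | 0.80 → 0.70 | −0.300 | −0.241 | 0.059²/0.51 = 0.7% | +0.3% |
| Symptoms | 0.80 → 0.60 | −0.400 | −0.264 | 0.136²/0.64 = 2.9% | +1.4% |
| Symptoms | 0.80 → 0.50 | −0.500 | −0.270 | 0.230²/0.75 = 7.1% | +3.5% |
| Symptoms (extreme) | 0.85 → 0.40 | −0.600 | −0.170 | 0.430²/0.84 = 22% | +10.5% |

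bc depends on the assumed Σ. For symptoms at 0.80 → 0.50, an autoregressive residual correlation of 0.9 per 8 weeks gives bc = −0.240. The inflation is then 0.260²/0.75 = 9.0%, or +4.4% in SE. Hence about 0-5% for moderate falls; this is a range, not an upper bound.

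**Step 3: compound-symmetry fallback.** Here bc is roughly the plain mean of the slopes. FEV1 0.85 → 0.70: 0.075²/0.51 = 1.1% variance (+0.5% SE). Symptoms 0.80 → 0.50: 0.15²/0.75 = 3.0% (+1.5% SE). These are smaller than under the planned unstructured matrix.

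**Step 4: power.** A two-sided 5% test with 90% power under the interaction model has power Φ[(1.960 + 1.282)/ratio − 1.960] under the stated model. A ratio of 1.019 gives 88.9%, 1.035 gives 88.0%, and 1.05 gives 87.0%.

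**Step 5: simulation.** Maximum-likelihood fits with n = 444 and 300 runs per scenario gave mean model-SE ratios of 1.000 (constant 0.85, no dropout), 1.005 (0.85 → 0.75, 10% random dropout) and 1.020 (0.80 → 0.60, 10% random dropout). These match Step 2.

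With about 20% dropout that depended on baseline and differed by arm, the mean estimates under no true effect were:

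| r: early → Week 48 | Common slope | Baseline-by-visit | Common-slope shift / SE |
|---|---|---|---|
| 0.85 → 0.75 | 0.0078 | −0.0030 | 0.0078/0.0689 = 0.11 |
| 0.80 → 0.60 | 0.0260 | −0.0012 | 0.0260/0.0827 = 0.31 |

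The two models differ by 0.011 and 0.027 SD, that is, about 0.01-0.03 SD.

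**The case against.** The strongest reply is that this is a modelling preference resting on assumed numbers. The protocol gives no SDs, visit correlations or power for either key secondary endpoint, and the loss vanishes if the slope is constant. **That stands**, and it limits the point to a conditional one.

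A reader might infer that precision at Week 48 is certainly lost, or that the loss can be stated as a number of patients. The documents support neither, because the size depends wholly on correlations and a within-patient covariance that they do not give.

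A reader might also infer that the Week 48 test is biased. The shift needs three things together: a changing slope, missing data related to baseline, and a pattern that differs by arm. Section 8.5 keeps data collected after treatment discontinuation, which limits missingness. Section 8.5.4 plans missing-data sensitivity analyses for the key secondary endpoints, including missing-not-at-random assumptions.

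The extra parameters are also not free everywhere. Section 8.5.2.1 repeats both analyses in five further eosinophil groups. The whole stratum below 300/µL is about 222 patients, and some groups are smaller. This stands and shapes the fix.

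Finally, the supplied documents hold no SAP, and a similar model leaves the exact symptom-score terms open. But the FEV1 model is written out term by term, so the point addresses a stated method and not a missing detail.

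**Conclusion.** The point holds as a minor one. The stated model constrains the baseline slope to be equal across visits although the controlled tests concern Week 48 alone. The cost is nil with a constant slope. Under moderate assumed falls in correlation it is roughly one power point for FEV1 and up to about three for the symptom score, from a 90% starting point. Only a steep assumed fall makes it material. The shift under baseline-related dropout that differs by arm is about a tenth to a third of a standard error in the scenarios tried. All sizes rest on assumed correlations, equal SDs, visit times, within-patient covariance and dropout. The stated model is not invalid; this is a cheap improvement worth pre-specifying.

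**What to change.** Add a baseline-by-visit interaction to the Section 8.5.2.1 model for FEV1 and for asthma symptom total score in the population with at least 300/µL. Do the same for the other endpoints referred to a similar model. State the term in the SAP before unblinding, which Section 8.1 allows.

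The cost is one parameter per additional visit: 7 − 1 = 6 for FEV1 and 24 − 1 = 23 for the symptom score. That is small against about 444 patients, and small beside the 24 × 25/2 = 300 covariance parameters the unstructured symptom model already carries. The Week 48 treatment contrast keeps its meaning, because baseline does not interact with treatment. If the slope is constant, almost nothing is lost. For the small eosinophil subgroups, pre-specify that the interaction may be dropped if the model does not converge, and where that step sits relative to the compound-symmetry fallback. No new data are needed.
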